### **12.5 Pregnancy Test**

Pregnancy test results will be provided in a listing.

### **12.6 Vital Signs**

Routine vital signs, including blood pressure, respiratory rate, temperature, and heart rate will be measured at Screening, Day 1 and Weeks 2, 4, 6, 8, 10, 12, 14, 16, 18, 20, 22, the End-of-Pegloticase-Infusions Visit (if applicable), the Week 24/End-of-Study/Early Termination Visit and the 3-month Post-Treatment Follow-up Visit (before any study drug infusion or scheduled blood draws). During the pegloticase treatment period study visits, vital signs should be taken before the pegloticase infusion and any time after the end of the infusion, but prior to subject's discharge/release from the site. In addition, if immediate infusion-associated events are noted during the infusion, vital signs will be monitored at least every 30 minutes until resolution or stabilization of the AE.

Blood pressure summaries are included in the exploratory analysis [Section 10.4.9](#).

Weight should be measured in kilograms or pounds without shoes and recorded at the Screening Visit, prior to pegloticase infusion on Day 1, at the Week 8 and 16 Visits, the non-infusion End of Pegloticase Infusions Visit (if applicable), the Week 24/End of Study/Early Termination Visit, and the 3 month Post Treatment Follow-up Visit.

Height will be collected at the Screening Visit only. Height is recorded in units of centimeters (cm). Body Mass Index (BMI) will be determined using the weight recorded in kg and the height measured at screening.

Descriptive summaries of observed and change from baseline values will be presented for each vital sign parameter except SBP, DBP and MAP by visit, using safety population by pegloticase treatment status (On Treatment, Post-Treatment, and Overall). Vital sign measurements that are monitored as a result of an infusion-associated event, will not be included in the descriptive summaries but will be presented in subject listings.

The following conversion factor will be used to convert any temperatures reported in degrees Fahrenheit to Celsius:

$$\text{Temperature (in } ^\circ\text{C)} = 5/9 (\text{Temperature [in } ^\circ\text{F]} - 32).$$

The following conversion factor will be used to convert any weights reported in pounds to kilograms:

$$\text{Weight [kg]} = \text{Weight [in lbs]} * 0.4536.$$

The following formula will be used to determine the BMI (in kg/m^2) using weight [in kg] and height [in m]:

$$\text{BMI} = \text{Weight} / ((\text{Height}/100) * (\text{Height}/100)).$$

### **12.7 ECG**

An electrocardiogram (ECG) will be performed at Screening and at the discretion of the Investigator thereafter. When a subject experiences an AE suspected to be an IR, a 12-lead ECG will also be performed.

This document is confidential.

The results will be recorded as normal or abnormal on the eCRF and all abnormal results will be evaluated as clinically significant (CS) or not clinically significant (NCS) by the investigator.

Using the safety population, a summary will be provided of subjects at Screening (using the count and percentage of subjects) with:

- Normal
- Abnormal NCS
- Abnormal CS

Percentages will be based on the number of subjects with an assessment completed.

Because the post-Screening ECGs are done at the discretion of the investigators, only the following summaries will be provided using the safety population:

- Incidence of post-Screening Abnormal ECGs (includes NCS and CS) findings
- Incidence of post-Screening Abnormal, Clinically Significant ECGs

For the post-Screening ECG summary, percentages will be calculated using the number of subjects in the safety population who have a post-screening ECG assessment.

ECG results will also be listed.

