#### **9.5.4.6 Electrocardiogram**

A 12-lead ECG will be performed at Screening and at the discretion of the Investigator thereafter. When a subject experiences an AE suspected to be an IR, a 12-lead ECG will also be performed.

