## 4 Study Design

### 4.1 Brief Description

This study is a Phase 4, multicenter, open-label, efficacy and safety study of pegloticase with uncontrolled gout who have undergone kidney transplantation. Twenty subjects are planned to be enrolled.

The study design will include: 1) a Screening Period, lasting up to 35 days; 2) a 24-week treatment period which includes an End-of-Study (Week 24)/Early Termination Visit; 3) a safety follow-up phone/email Visit 30 days after the last infusion; and 4) a 3-month post-treatment follow up visit.

Samples for measurement of sUA levels will be collected at the Screening Visit, prior to each infusion, 15-60 minutes after the end of each infusion and at the End-of-Study/Early Termination Visit. Additional samples for sUA levels will be collected at non-infusion Visits at Weeks 21 and 23.

Subjects who meet all of the inclusion criteria and none of the exclusion criteria during Screening will be enrolled at the Day 1 Visit to receive pegloticase 8 mg administered IV every 2 weeks from Day 1 through Week 22, inclusive. During this 24-week treatment phase, subjects who meet the individual subject sUA stopping rule (pre-dose sUA level >6 mg/dL at 2 consecutive study visits beginning with the Week 2 Visit) or discontinue treatment for any other reason will complete the End-of-Pegloticase-Infusions Visit procedures within 2 weeks and be encouraged to continue to participate in all visits through the end of the study. Subjects will return for regularly scheduled visits and will complete all study visit procedures with the exception of the pegloticase infusion and IR prophylaxis. After the Week 24 Visit (or End-of-Pegloticase-Infusions Visit [if applicable]), subjects should resume regular care for gout per the judgment of the treating physician, including resumption of urate-lowering therapy (ULT) upon pegloticase discontinuation, if appropriate. Subjects will have a 3-Month Follow-up visit to assess clinical status, including sUA levels.

On days of scheduled infusions, pegloticase will be administered after all pre-dose visit assessments have been completed. The date and start and stop time of infusion will be recorded. The date of the first dose of pegloticase is defined as Day 1. All subsequent doses and study visits will be scheduled based on the Day 1 visit date.

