### **6.2. Safety Population**

The safety population will include all subjects who receive at least 1 dose of pegloticase; therefore it will be equivalent to the ITT population.

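### SAP 12.7 calls the percentage of abnormal post-Screening ECGs an incidence, but it ignores the Screening result and first dose and describes only the subjects who were tested

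*SAP*

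**What the plan says.** SAP 12.7 sets the collection rule: "An electrocardiogram (ECG) will be performed at Screening and at the discretion of the Investigator thereafter". Protocol 9.5.4.6 adds the one mandated trigger after that: "When a subject experiences an AE suspected to be an IR, a 12-lead ECG will also be performed". SAP 12.7 repeats this trigger.

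Each ECG is recorded as normal or abnormal, and an abnormal one is graded not clinically significant (NCS) or clinically significant (CS). The Screening results are tabulated in these three categories. For later ECGs the SAP says: "Because the post-Screening ECGs are done at the discretion of the investigators, only the following summaries will be provided using the safety population". There are two such summaries. One is headed "Incidence of post-Screening Abnormal ECGs (includes NCS and CS) findings"; the other covers the CS findings alone. For both, "percentages will be calculated using the number of subjects in the safety population who have a post-screening ECG assessment". All ECG results are also listed.

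Neither summary is tied to the subject's Screening category or to the date of first dose, and no shift from Screening is planned. SAP 6.2 defines the population: "The safety population will include all subjects who receive at least 1 dose of pegloticase". The planned size is in SAP 4.1: "Twenty subjects are planned to be enrolled".

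**The concern.** Two features pull the figure away from what its label promises.

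- **Numerator.** An incidence should count findings that arise on study. Exclusion criterion 7 (Protocol 9.3.2) bars certain decompensated or uncontrolled cardiac conditions but not an abnormal ECG, so subjects can enter with one. If such a subject has any later ECG and the finding persists, it is counted. Because the cut-off is Screening and not first dose, a discretionary ECG taken before the first infusion could count as well.
- **Denominator.** The subjects with a later ECG are those with a suspected IR and those for whom an investigator chose to order one. A percentage among them describes ECG yield in a selected group.

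The SAP treats similar data differently elsewhere. Laboratory results get shift tables against baseline (SAP 12.4). Vital signs taken because of an infusion-associated event are kept out of the summaries and only listed (SAP 12.6). IR and cardiovascular tables are produced only if at least 5 subjects are affected (SAP 12.3.3.1 and 12.3.3.2), whereas the ECG percentage has no such floor.

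SAP 5.5 names ECG as a safety endpoint, and SAP 13 allows periodic summaries to support publications, when fewer subjects may have been tested. With one arm, there is no control column to show the reader that the percentage reflects selection.

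**Working it through.** The documents give no expected number of post-Screening ECGs and no expected percentage, so there is no plan figure to reproduce. The check is on how far the label can mislead.

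**Inputs from the documents**
- N = 20 dosed subjects (SAP 4.1 and 6.2).
- IR rate 22/85 = 25.9% in the Phase 3 studies (Protocol 7.1.2).
- IR rate 8% in a post-hoc application of the serum uric acid stopping rule (Protocol 7.1.2).

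**Assumptions**
- x is the number of subjects with at least one abnormal post-Screening ECG; m is the number with any post-Screening ECG.
- d is the share of subjects without an IR who get a discretionary ECG. It is not stated; 0 to 50% is shown.
- The reported-IR rates stand in for suspected IRs, which could be more frequent.

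**Step 1: denominator.** The SAP prints x/m. Over all dosed subjects the figure is x/20. The ratio is (x/m)/(x/20) = 20/m, whatever x is: 10 at m = 2, 5 at m = 4, 3.3 at m = 6, 2 at m = 10, 1.3 at m = 15. It reaches 3 only if at most 6 of 20 subjects are tested (20/7 = 2.9).

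**Step 2: plausible m.** With r for the IR rate, m = 20 × [r + (1 − r) × d].

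| d (assumed) | m at r = 22/85 | 20/m | m at r = 8% | 20/m |
|---|---|---|---|---|
| 0 | 5.2 | 3.9 | 1.6 | 12.5 |
| 10% | 6.7 | 3.0 | 3.4 | 5.8 |
| 25% | 8.9 | 2.2 | 6.2 | 3.2 |
| 50% | 12.6 | 1.6 | 10.8 | 1.9 |

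The first row is the extreme in which IRs are the only trigger.

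**Step 3: what the reader would see.** Suppose 4 subjects are tested and 1 is abnormal. The SAP prints 1/4 = 25% (exact 95% CI 0.6% to 80.6%). Over all dosed subjects it is 1/20 = 5% (0.1% to 24.9%).

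**Step 4: numerator.** Keep the denominator at those tested. Assume a share q was abnormal at Screening and remains so, and that 20% of the rest become abnormal. The SAP counts q + (1 − q) × 0.20; new findings are (1 − q) × 0.20.
- q = 20%: 0.20 + 0.80 × 0.20 = 36% reported, 16% new, ratio 2.25.
- q = 30%: 0.30 + 0.70 × 0.20 = 44% reported, 14% new, ratio 3.1.
- q = 50%: 0.50 + 0.50 × 0.20 = 60% reported, 10% new, ratio 6.0.

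Nothing in the documents gives q or the 20%. These lines show only that the omission can matter as much as the denominator.

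**The case against.** The denominator is stated openly and follows the SAP's general convention (SAP 16.2.5.2), under which percentages are taken over subjects with an observation unless otherwise noted. That stands: x/m is a correct percentage of those tested, and the fault lies in its label. The same section also says that choosing a denominator needs care and that it is usually the number exposed, so the convention does not settle the matter.

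A reader might infer that these ECGs are mostly done for a suspected reaction. The documents do not say so. A suspected IR is the only mandated trigger, but the reason the SAP gives for its limited summaries is investigator discretion, and no frequency or split is given.

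A reader might also infer that the SAP's figure is wrong by a known multiple and that x/20 is the true incidence. That is not supported either. x/20 counts every untested subject as normal and can understate a safety finding, and the multiple depends on an unknown m.

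On the numerator, the SAP does not say that it means to count pre-existing findings; it fails to exclude them. In 20 subjects the listings allow a comparison by hand.

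The strongest point concerns consequence. Under Protocol 9.5.4.1.1.1 abnormal diagnostic results can be AEs, with findings that are not a clinically significant change from baseline excluded. New clinically significant ECG changes should therefore appear in the treatment-emergent AE tables over the whole safety population (SAP 12.3.2), and cardiovascular events are adjudicated. Protocol 9.6.1.5 does not list ECG as a safety endpoint; only SAP 5.5 does. This limits the harm but leaves the table mislabelled.

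**Conclusion.** The point holds as one of labelling and missing conditioning. What SAP 12.7 calls an incidence is a percentage among subjects who had an unscheduled ECG, with no allowance for the Screening result or for first dose.

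Against an all-dosed denominator it is larger by 20/m. That is about 1.6 to 3.9 at the Phase 3 IR rate and 1.9 to 12.5 at 8%, with the upper ends reached only if IRs are the sole trigger and the lower ends if half of the remaining subjects are also tested. These ranges rest on the protocol's reported-IR rates and an assumed share of discretionary ECGs. The numerator effect, 2.25 to 6.0 in the illustration, rests wholly on assumed rates.

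Neither x/m nor x/20 is unbiased, which is why the reader needs x, m and N together. The impact is limited to a descriptive safety table in a single-arm study without formal testing.

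**What to change.** In SAP 12.7:

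1. Count only ECG findings after the first dose that are new or worse in category (normal, NCS, CS) than at Screening, and show them as a shift table. If a subject has a later ECG before first dose, SAP 8.2.1 already defines which observation is baseline and asks for time to be considered on Day 1.
2. Print x, m and N together, for example 1 abnormal, 4 tested, 20 dosed.
3. Replace the word incidence with a label saying that the percentage is among subjects with a post-Screening ECG. Alternatively, drop the percentages and list only, as SAP 12.6 does for vital signs taken because of an infusion-associated event.
4. Flag ECGs triggered by a suspected IR, using the AE data. Do not require a reason for discretionary ECGs unless it is collected; the documents do not show that it is.

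The cost is SAP wording and one more small table from results already recorded. The drawback is that a category shift misses a different abnormality within the same category, such as one NCS finding replaced by another; the listing remains the place to see that.

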## **12.8. Physical Examination**

A complete physical examination will be performed at the Screening Visit and will include assessments of head, eyes, ears, nose, and throat (HEENT), heart, lungs, abdomen, skin, extremities, neurological status and musculoskeletal system, and for presence of tophi, as well as gout history and symptom severity. A targeted physical examination (for joint and skin evaluation and assessment of AEs) will be conducted based on potential risk for or occurrence of AEs at Day 1, and prior to administration of infusion at Weeks 4, 8, 12, 16, and 20, the End of Pegloticase Infusions Visit (if applicable), Week 24/End of Study/Early Termination Visit and 3 month Post Treatment Follow Up Visit; at a minimum this should include heart, lungs, and abdomen. Clinically significant findings from the targeted physical examinations will be recorded as AEs.

Physical examination data will be listed. No summarizations of the physical examination data will be presented.

This document is confidential.

### **13. Interim Analyses**

No formal interim analysis is planned for this study. Efficacy and safety data may be summarized periodically throughout the study to support scientific publications. Additionally, safety data will be summarized regularly for safety monitoring. Final analysis will occur when all subjects have completed the study.

No adjustments to type I error rates or nominal confidence levels for confidence intervals will be made to account for these summaries.

This document is confidential.

#### **14. Changes from Analysis Planned in Protocol**

The analysis population definitions have been changed:

- Per the protocol, only the modified Intent-to-Treat (mITT) population was defined as all subjects who receive at least 1 dose of pegloticase. The mITT population was planned to be used for analysis of ADA, efficacy and safety data.
- For the purposes of ease of future integration with other pegloticase studies, the mITT definition has been removed, and instead has been replaced by the Intent-To-Treat (ITT) population definition (for the analysis of ADA and efficacy data) and the safety population definition (for the analysis of safety data). Both the ITT and the safety population are defined as all subjects who receive at least 1 dose of pegloticase.

The phrasing of the safety endpoints relating to laboratory tests and vital signs has been updated from "Laboratory tests" and "Vital signs" to "Laboratory tests: change from baseline to each scheduled assessment" and "Vital signs: change from baseline to each scheduled assessment," respectively.

This document is confidential.

## 16. Programming Considerations

### 16.1. General Considerations

- All TLFs will be produced in landscape format.
- All TLFs will be produced using the Courier New font, size 8
- The data displays for all TLFs will have a minimum 1-inch margin on all 4 sides.
- Headers and footers for figures will be in Courier New font, size 8.
- Legends will be used for all figures with more than 1 variable, group, or item displayed.
- TLFs will be in black and white (no color)
- Specialized text styles, such as bolding, italics, borders, and shading will not be used in the TLFs, unless otherwise specified. On some occasions, superscripts 1, 2, or 3 may be used.
- Only standard keyboard characters will be used in the TLFs. Special characters, such as non-printable control characters, printer-specific, or font-specific characters, will not be used. Hexadecimal-derived characters will be used, where possible, if they are appropriate to help display math symbols (e.g.,  $\pi$ ). Certain subscripts and superscripts (e.g.,  $m_2$ ,  $C_{trough}$ ) will be employed on a case-by-case basis.
- Mixed case will be used for all titles, footnotes, column headers, and programmer-supplied formats, as appropriate.

### 16.2. Table, Listing, and Figure Format

#### 16.2.1. General

- Headers and footers for figures will be in Courier New font, size 8 which is the smallest acceptable point size for the Regulatory Authorities.
- Legends will be used for all figures with more than 1 variable, group, or item displayed.
- Tables, Figures and Listings (TFLs) will be in black and white (no color), unless otherwise specified
- Specialized text styles, such as bolding, italics, borders, shading, and superscripted and subscripted text, will not be used in the TFLs, unless otherwise specified. On some occasions, superscripts 1, 2, or 3 may be used (see below).
- Only standard keyboard characters will be used in the TFLs. Special characters, such as non-printable control characters, printer-specific, or font-specific characters, will not be used. Hexadecimal-derived characters will be used, where possible, if they are appropriate to help display math symbols (e.g.,  $\mu$ ). Certain subscripts and superscripts (e.g.,  $cm_2$ ,  $C_{max}$ ) will be employed on a case-by-case basis.
- Mixed case will be used for all titles, footnotes, column headers, and programmer-supplied formats, as appropriate.

#### 16.2.2. Headers

- All output should have the following header at the top left of each page:
- Horizon Therapeutics Ireland, DAC, Protocol HZNP-KRY-406
- All output should have Page n of N at the top or bottom right corner of each page. TFLs are internally paginated in relation to the total length (i.e., the page number should appear sequentially as page n of N, where N is the total number of pages in the table).

This document is confidential.

- The date output was generated should appear along with the program name as a footer on each page.

#### 16.2.3. Display Titles

- Each TLF is identified by the designation and a numeral. (i.e., Table 14.1.1). ICH E3 numbering is strongly recommended, but sponsor preferences are obtained before final determination. A decimal system (x.y and x.y.z) are used to identify TFLs with related contents. The title is centered. The analysis set are identified on the line immediately following the title. The title and table designation are single spaced. A solid line spanning the margins will separate the display titles from the
- Column headers. There will be 1 blank line between the last title and the solid line.

Table x.y.z  
First Line of Title  
Second Line of Title if Needed  
(Analysis Set)

#### 16.2.4. Column Headers

- Column headings are displayed immediately below the solid line described above in initial upper-case characters.
- In the case of efficacy tables, the variable (or characteristic) column will be on the far left followed by the treatment group columns and total column (if applicable). P-values may be presented under the total column or in separate p-value column (if applicable). Within-treatment comparisons may have p-values presented in a row beneath the summary statistics for that treatment.
- For numeric variables, include “unit” in column or row heading when appropriate.
- Analysis set sizes will be presented for each treatment group in the column heading as (N=xx) (or in the row headings, if applicable). This is distinct from the ‘n’ used for the descriptive statistics representing the number of subjects in the analysis set.
- The order of treatments in the tables and listings will be Placebo first in the case of placebo controlled studies and Active comparators first in the case of active comparator trials, followed by a total column (if applicable).

#### 16.2.5. Body of the Data Display

##### 16.2.5.1. General Conventions

Data in columns of a table or listing are formatted as follows:

- Alphanumeric values are left-justified;
- Whole numbers (e.g., counts) are right-justified; and
- Numbers containing fractional portions are decimal aligned.

This document is confidential.

### 16.2.5.2. Table Conventions

- Units will be included where available
- If the categories of a parameter are ordered, then all categories between the maximum and minimum category are presented in the table, even if n=0 for all treatment groups in a given category that is between the minimum and maximum level for that parameter. For example, the frequency distribution for symptom severity would appear as:

Severity Rating	N
mild	0
moderate	8
severe	3

Where percentages are presented in these tables, zero percentages will not be presented and so counts of 0 will be presented as 0 and not as 0 (0%).

- If the categories are not ordered (e.g., Medical History, Reasons for Discontinuation from the Study, etc.), then only those categories for which there is at least 1 subject represented in 1 or more groups are included.
- An Unknown or Missing category are added to each parameter for which information is not available for 1 or more subjects.
- Unless otherwise specified, the estimated mean and median for a set of values are printed out to 1 more significant digit than the original values, and standard deviations are printed out to 2 more significant digits than the original values. The minimum and maximum should report the same significant digits as the original values. For example, for systolic blood pressure:

N	XX
Mean	XXX.X
Std Dev	X.XX
Median	XXX.X
Minimum	XXX
Maximum	XXX

- P-values are output in the format: "0.xxx", where xxx is the value rounded to 3 decimal places. Every p-value less than 0.001 will be presented as <0.001. If the p-value are less than 0.0001, then present as <0.0001. If the p-value is returned as >0.999, then present as >0.999
- Percentage values are printed to one decimal place, in parentheses with no spaces, one space after the count (e.g., 7 (12.8%), 13 (5.4%)). Pre-determine how to display values that round down to 0.0. A common convention is to display as '<0.1', or as appropriate with additional decimal places. Unless otherwise noted, for all percentages, the number of subjects in the analysis set for the treatment group who have an observation will be the denominator. Percentages after zero counts should not be displayed and percentages equating to 100% are presented as 100%, without decimal places.

This document is confidential.

- Tabular display of data for medical history, prior/concomitant medications, and all tabular displays of adverse event data are presented by the body system, treatment class, or SOC with the highest occurrence in the active treatment group in decreasing order, assuming all terms are coded. Within the body system, drug class and SOC, medical history (by preferred term), drugs (by ATC1 code), and adverse events (by preferred term) are displayed in decreasing order. If incidence for more than 1 term is identical, they should then be sorted alphabetically. Missing descriptive statistics or p-values which cannot be estimated are reported as “-”.
- The percentage of subjects is normally calculated as a proportion of the number of subjects assessed in the relevant treatment group (or overall) for the analysis set presented. However, careful consideration is required in many instances due to the complicated nature of selecting the denominator, usually the appropriate number of subjects exposed. Describe details of this in footnotes or programming notes.
- For categorical summaries (number and percentage of subjects) where a subject can be included in more than one category, describe in a footnote or programming note if the subject are included in the summary statistics for all relevant categories or just 1 category and the criteria for selecting the criteria.
- Where a category with a subheading (such as system organ class) has to be split over more than one page, output the subheading followed by “(cont)” at the top of each subsequent page. The overall summary statistics for the subheading should only be output on the first relevant page.

